This protocol is intended for a multicenter open label experimental, randomized controlled trial on the efficacy and safety of using first line AEDs as substitution therapy in childhood drug-resistant epilepsy. It will prospectively follow 100 children up during 14 weeks that consist of baseline, intervention, and post-intervention phases. While the intervention consists of 6 steps, as described at the Figure 1 below.

[figure not shown]

Figure 1. Timeline of the intervention phases

The study will be conducted at pediatric outpatient clinic of 3 referral hospitals in Jakarta, Cipto Mangunkusumo Hospital, Harapan Kita Hospital and Fatmawati Hospital. Children who are diagnosed with drug-resistant epilepsy receiving levetiracetam or topiramate will be enrolled in the study. Enrollment begins as soon as the research ethics committee approval is obtained from The Ethics Committee of The Faculty of Medicine, University of Indonesia-Cipto Mangunkusumo Hospital. The study will be closed after the last recruited patient has been followed up for the required 14 weeks.

All recruited children will be examined for monitoring at the hospital where the intervention is initiated. To avoid selection bias, all patients who met the inclusion criteria are divided into two groups, the intervention and control groups. Prospective participants and their parents will be provided with information related to the study. Patients will then fill out an information sheet containing demographic data, comorbidities, developmental history, school history, history of drug consumption, as well as history of seizures and patient complaints. All the data will be extracted and recorded on the case report form. Patients and their parents should be informed that participation is voluntary and they are free to withdraw from the study at any time. They should also be informed that refusal to participate or withdraw from the study will not affect the quality of treatment received. In the event of their withdrawal, it will be explained that the data collected so far is irrevocable, and we will seek consent to use such data in the final analysis if necessary.

Study procedure

Study procedures are depicted in Figure 2. The patients who are eligible for the study and have given their consents, will be enrolled, divided into 2 groups, the intervention and control, then start the 3-day baseline phase. In this phase, data such as demographic, clinical characteristic

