including seizure frequency, seizure type, seizure onset, medication history, family history of seizure, and also developmental stages, will be recorded from electronic medical record. Besides, the CT-scan or MRI are also collected from the same source. After that, their quality of life will be assessed by QOLCE-55 validated questionnaire through self-guided report. Furthermore, the laboratory investigation and EEG will be performed.

The next phase is intervention phase, started from initial step and ended by the maintenance of new combination therapy, which takes with overall 12 weeks. Initially, the substitution drugs with each initial dose are consumed. The drugs consist of valproic acid for the generalized and carbamazepine for focal epilepsies. On the other hand, the control group will take lamotrigine or clobazam for generalized and oxcarbazepine for focal ones. The phase continuous to titration dose, in which, the dose is raised gradually until it causes 50% of seizure reduction, and the next step is maintained the dose for about 2 weeks.

The following is tapering-off and after that stopping the substituted drug, levetiracetam or topiramate, which is determined by considering individual condition. Yet, if the seizures increase more than one and a half time of the previous frequency during the phases, the intervention will be ended immediately. On the contrary, if the condition is better, then the children go to the maintenance of new combination, that is the substitution drug and the old drugs in which the seizures do not go up or even better keep going down. The children who complete all of the phases are categorized as responder. In case if the intervention is ended, the subjects will be given the former combination therapy with adjusted doses in order to decrease the seizures until reaching the pre-intervention condition. The subjects are categorized as non-responder, and will be dropped-out. The other criteria of drop-out are resignation, non-compliance of study procedure, and death in term of other causal not related to the study. While in term of lost to follow-up, is intended for those who do not attend the study without any possible reasons.

[figure not shown]

Figure 2. flow-chart of the study

Maintenance the dose of the new combination therapy that consist of the new drug and

Maintenance

old drug after stopping the substituted drug

Inclusion criteria

- 1. Children age at 1 18 years old

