The test is performed in hospitals' laboratory where the study take place and is done twice, at the baseline and post intervention phase. The order of the blood test consists of complete blood test, liver function test including alanine and aspartate transaminase, kidney function test including urea and creatinine, and also blood electrolyte that consist of natrium, kalium and calcium. The laboratory professional takes the blood from vein of the arm. The subjects are seated or lying down, accompanied by the parents, while for the younger children, they seat on his/her parents' lap or position that make them feel comfortable. Older children may be asked to make a fist and then will be tied by a rubber band around his/her arms. After that, the needle is inserted the needle until the blood is drawn. The laboratory worker will take the needle since the amount of blood is enough and puts an adhesive bandage over the site. The next step is analyzes of the sample and the result will be issued for about 1-2 days both printed or provided on the electronic medical record.

Electroencephalography Examination

The EEG examination is operated two times, at the baseline and post intervention phase, with high density machine (Caldwell Easy III) is done twice, pre- and post-intervention. The machine will operate for about 45 minutes including 5 minutes each for eye-open and eye-close in every subjects. Beginning with acquisition, EEG recordings use standard parameter to analyze brain activity at various frequencies to gain good quality and artefact-free result. The printed results of the EEG is available for about 4-7 days after the examination.

Data collection

All relevant data will be recorded, by nominated member(s) of the research team, on a case report form (CRF). Each participant will have a CRF and be assigned a unique identification number.

Baseline data

At entry into the study, the following baseline information will be recorded in the CRF:

- unique patient identification number contact telephone number and/or email address
- date of entry into the study
- eligibility for study entry based on inclusion/exclusion criteria
- age at study entry, in years and months
- gender
- weight and height
- seizure type (eg, generalized tonic clonic, absence, myoclonic and partial)
- the age at diagnosis and duration of epilepsy
- seizure frequency or average number of seizures per month

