- current anticonvulsant(s) with doses and formulation and its side effect (if presents)
- other medications and its side effect (if presents)

- first recognized seizure date
- prior EEG and laboratory which has been performed at the baseline phase
- physical examination

Follow-up data

Follow-up data will be collected during regularly scheduled clinic visits (per 2 weeks). This information will be obtained from the participants' diary card. Important information to be collected at follow-up will include:

- physical examination
- adverse drug reaction of the substitution therapy that happen
- seizure's frequency
- type of seizure
- complaint

Outcome evaluation

- a. The difference in responders was the difference in the percentage of responders in the group that used first line OAE again as substitution therapy and those that used standard therapy. Responders are subjects who experience a decrease frequency of seizure more than or equal to 50% of the initial seizure. Frequency of seizure is the number of seizures that occur within 1 month. In previous studies, it was said that the frequency of seizures was said to have decreased significantly or was said to respond if the seizures were reduced by 50% or more from the initial seizure. ^{19, 29} Based on this, researchers will categorize the frequency of seizures into:
 - Responder: there is a decrease in the frequency of seizures by 50% or more than before
 - Non-responder: namely the frequency of seizures remains or decreases but not up to 50% of the initial seizure frequency or the frequency is more than before

Furthermore, the proportion in the form of the percentage of respondents in the two groups is calculated and differentiated, therefore it is classified into two groups:

- Different : when a significant difference is shown in difference of proportion test of the 2 unpaired groups.
- Not different: when there is no significant difference is shown in difference of proportion test of the 2 unpaired groups.

- b. Differences in quality of life: quality of life assessment using QOLCE-55 instrument. The average of each function (cognitive, emotional, social and physical functions) and the average of the total functions are assessed. This variable is categorized into:
 - Different, if there is a difference in the average quality of life
 - Not different, if there is no difference in the average quality of life
- c. Differences in electroencephalography appearance

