P1 proportion of reduced seizure on the new drug (the proportion of reduced seizure on the standard drug in addition to the minimal difference that is considered significant)= 0.7 + 0.25 = 0.95

Q1
$$1 - P1 = 1 - 0.95 = 0.5$$

P
$$(P1 + P2) / 2 = (0.95 + 0.7) / 2 = 0.825$$

Q
$$1-P = 1-0.825 = 0.175$$

In this study, it was found that the proportion of seizure reduction on standard drugs was 70%.³⁰ Therefore the equation:

$$n1 = n2 = \left(\frac{1,96\sqrt{2(0,825)(0,175)} + 0,84\sqrt{(0,95)(0,5) + (0,7)(0,3)}}{0,25}\right)^2 = 49,56 = 50$$

$$n\ 2\ groups=100$$

Based on the formula above, 100 research subjects are required. An additional of 10% from the total number of subjects are needed as there is a possibility of those dropping out, therefore a total of 110 subjects are needed in this study.

Statistical Analysis

- 1. Analysis of differences in the proportion of responders (primary outcome), differences in EEG appearance (secondary outcome) in pediatric epilepsy patients who are resistant to the combination of second line OAE between those who reused first line OAE as substitution therapy and those who used standard therapy. Data type is categorical. Data is analyzed the Chi-square statistical test, if it does not meet the requirements then an alternative test is performed, known as Fisher's multiple test. The significance level (α) is 5% and the research confidence level is 80%. If p value ≤ α is obtained, this means H0 is rejected, which means that there is a difference seen in seizure frequency between reusing first line OAE as substitution therapy and standard therapy.
- 2. Analysis of differences in the mean quality of life with an unpaired T test if the data distribution is normal or Mann-Whitney if data distribution is not normal
- 3. To assess drug effectiveness, the analysis used was the difference in actual failure between those using first line OAE as substitution therapy and those using standard therapy (primary outcome). Formula:

$$ARR = CER - EER$$

CER: the incidence of increased seizure frequency in the standard therapy group ERR: the incidence of increased seizure frequency in the group in substitution therapy with 1st line OAE The increase in seizure frequency in this study shows therapy

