This test will use 2 analyses known as intention to treat analysis and per-protocol analysis. Intention to treat analysis means that all research subjects who have been randomized are included in the analysis according to their initial allocation regardless of whether or not the subject is taking the drug/therapy being tested or a placebo, or whether these subjects died before taking the drug being tested. Subjects who did not

failure.

take medication, lost to follow-up, and who moved to another group, are considered failures of their original group.

Whereas per protocol analysis only includes subjects who complete the research to the end.

- 4. Analysis of the difference in time to achieve a decrease in seizure frequency with the chisquare test or if it does not meet the requirements, an alternative test is performed, namely the Mann-Whitney test
- 5. Analysis of clinical characteristics, side effects of OAE, and laboratory findings of complete blood count (hemoglobin, hematocrit, leukocytes, platelets, and type count), liver function (SGOT and SGPT), kidney function (urea and creatinine), and blood electrolytes (sodium, potassium, calcium, chloride) in pediatric epilepsy patients who are resistant to combination second OAE who re-use first line OAE as substitution therapy and who use standard therapy (secondary outcome). All existing data is processed and presented in a table consisting of mean and standard deviation or median and inter-quartile range, as well as frequency distribution.
- 6. Analyzing factors that affect the decrease in the frequency of late seizures (age, seizure onset, seizure type, family history of seizures, developmental delays, history of OAE, initial seizure frequency, initial EEG, brain structural abnormalities) in pediatric patients with resistant epilepsy combination of second line OAE who re-use first line OAE as substitution therapy (secondary outcome).

Data is categorical. Data is analyzed using Chi-square statistical test, if results do not meet the requirements then an alternative test will be performed, known as Fisher's multivariate test and further analyzed with multivariate test and logistic regression analysis. The significance level (α) is 5% and the research confidence level is 80%. Results will show statistically related if value of $p \le \alpha$ is obtained.

Ethics and dissemination

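### The primary chi-square pools drug pairings set by epilepsy type, with no adjustment for type and no result by type; the test is valid, but a type-stratified analysis with by-type results costs almost nothing

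*Combined protocol and SAP*

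**What the plan says.** Study procedure assigns drugs by epilepsy type in both arms. For the first-line arm: "The drugs consist of valproic acid for the generalized and carbamazepine for focal epilepsies". For the other arm: "the control group will take lamotrigine or clobazam for generalized and oxcarbazepine for focal ones". No rule is given for choosing between the two control drugs in generalized epilepsy.

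Outcome evaluation item a declares the arms different "when a significant difference is shown in difference of proportion test of the 2 unpaired groups". Statistical Analysis item 1 gives the test: "Data is analyzed the Chi-square statistical test, if it does not meet the requirements then an alternative test is performed", the alternative being a Fisher-type test. Neither place names a stratum, a covariate, a by-type estimate or an interaction test.

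The trial is called randomized, but on the method Study Design says only that "all patients who met the inclusion criteria are divided into two groups, the intervention and control groups". The readable text describes no stratification; the flow chart (Figure 2) is not available to us.

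The baseline list under Data collection includes "seizure type (eg, generalized tonic clonic, absence, myoclonic and partial", which is seizure type. A generalized/focal epilepsy field is not listed, although type must be known before a drug can be chosen. Seizure type is otherwise used only in the factor analysis (Outcome evaluation item e; Statistical Analysis item 6). Item 6 is worded for children "who re-use first line OAE as substitution therapy (secondary outcome", so it neither adjusts nor splits the comparison between arms.

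**The concern.** The responder difference is a weighted average over different drug contrasts: valproic acid against lamotrigine or clobazam, and carbamazepine against oxcarbazepine. The weights are whatever type mix happens to be recruited. Two things follow.

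- Type may be prognostic. The Introduction names seizure types among possible contributors to drug resistance, and the plan lists seizure type as a factor for seizure reduction. If the arms differ in type by chance, part of the observed difference reflects case mix, and the planned test does not correct for it.
- If one pairing favours first-line drugs and the other does not, the pooled figure describes neither. With no by-type result planned, a reader could not tell.

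**Working it through.** **Inputs.** From Sample size: control responder rate 0.70, difference 0.25 (so 0.95 on first-line drugs), alpha 5% with Z = 1.96, Z beta = 0.84, 50 per group. The documents give no type mix and no type-specific rates. All such values below are assumptions.

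**The plan's own figure.** The printed inputs, including Q1 = 0.5, give
[(1.96 × √(2 × 0.825 × 0.175) + 0.84 × √(0.95 × 0.5 + 0.7 × 0.3)) / 0.25]² = [(1.053 + 0.695) / 0.25]² = 48.9, against the stated 49.56, rounded to 50. (With Q1 = 1 − 0.95 = 0.05 the same formula gives 35.0. That is a separate matter, but it explains why power at 50 per arm exceeds 80%: about 92% by the normal approximation and 94.8% by simulation.) One control rate and one difference serve both types.

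**Type I error.** 200,000 simulated trials per scenario, 50 per arm, unstratified 1:1 allocation. With null rates of 0.85/0.55 or 0.90/0.50 (generalized/focal) and focal shares of 30%, 50% and 70%, the pooled chi-square rejects in 4.9% to 5.1% of trials and CMH in 4.9% to 5.0%. Both are valid.

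**Chance imbalance.** The probability that the arms differ by at least 5 of 50 children in type is 37% at a 50:50 mix and 33% at 30:70. A gap of 10 or more children occurs in about 6% and 4%.

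**What an imbalance does.** Shift in the crude difference = imbalance × prognostic gap.
- 10 points × a 20-point gap = 2 points.
- 10 points × a 40-point gap (50%/90%) = 4 points.
- 20 points × a 40-point gap = 8 points, and in such trials the pooled test rejects a true null about 11% of the time.

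For scale, the standard error of the crude difference is about √(2 × 0.7 × 0.3 / 50) = 9 points.

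**Power, pooled chi-square versus CMH, 50:50 mix.**

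| Control rates by type | Treated rates by type | Average control | Pooled | CMH |
|---|---|---|---|---|
| 70/70 | 95/95 | 70% | 94.8% | 93.9% |
| 60/80 | 92/98 | 70% | 94.8% | 94.6% |
| 85/55 | 99/91 | 70% | 94.8% | 95.4% |
| 70/70 | 90/90 | 70% | 73.5% | 72.3% |
| 60/80 | 80/100 | 70% | 73.4% | 75.3% |
| 30/70 | 50/90 | 50% | 54.4% | 61.2% |
| 20/70 | 45/95 | 45% | 73.6% | 85.4% |

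The first three rows match the protocol's 70% versus 95%; there CMH changes power by −0.9 to +0.6 points. Gains of 7 to 12 points appear only in the last two rows.

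**Effects that differ by type (50% focal).**
- 25 points in generalized epilepsy only: 31% power with either test.
- +20 points in one type and −20 in the other: about 5% with either test.

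Stratifying the test does not reveal these; by-type results can. With 25 children per arm in each type, by normal approximation:
- Opposite effects (70% to 90% and 70% to 50%): the SE of the difference between risk differences is √[(0.21 + 0.09 + 0.21 + 0.25) / 25] = 0.174. Then 0.40/0.174 = 2.29, giving interaction power of about 63%.
- Effect in one type only (70% to 95% and 70% to 70%): SE √[(0.21 + 0.0475 + 0.21 + 0.21) / 25] = 0.165. Then 0.25/0.165 = 1.52, giving about 33%.
- 95% CI half-width within one type at 70% versus 95%: 1.96 × √(0.2575/25) = 20 points. Power within that type is 65%.

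**The case against.** The best defence is that pooling answers the stated question. The objective compares first-line with second-line substitution as a strategy, with the drug fitted to the child, and the unadjusted test is valid for that. This stands. Adjusting is an improvement, not the repair of an error.

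A reader might infer more from the design than the documents support:

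- *That the crude comparison confounds type with treatment.* Under randomization, chance imbalance is already included in the 5% error rate. What remains is a conditional shift in the trial actually run, usually small beside a 9-point standard error.
- *That stratifying buys substantial power.* The 7 to 12 point gains need control rates averaging 45% to 50%, against the protocol's 70%, and strong type differences.
- *That CMH solves the pooling of drug pairings.* It still yields one p-value. Only the by-type results address that, and they are imprecise.
- *That there are exactly two comparisons, with type already on the case report form.* Generalized controls may receive either of two drugs, and the listed item is seizure type.

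It can also be said that seizure type already enters a logistic regression. As worded, that model covers first-line patients only, so it does not answer this point.

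**Conclusion.** The point holds as a low-cost improvement. The plan's primary test is valid for the overall strategy. It leaves chance imbalance in a factor that sets the treatment pairing uncorrected (a gap of 10 points or more in about 33% to 37% of trials for mixes from 30:70 to 50:50), and no by-type result is planned that could show whether the pairings agree. At the protocol's 70% versus 95%, the effect on power is about −1 to +1 point, so the case rests on conditional balance and interpretation. These sizes assume 50 per arm and unstratified 1:1 allocation. The type mix and type-specific rates are assumed throughout, and the absence of stratification is judged from the text without Figure 2.

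**What to change.** - Add an explicit generalized/focal field to the case report form, completed before allocation.
- In Statistical Analysis item 1, make the primary test a Cochran-Mantel-Haenszel test stratified by that field (exact version if cells are sparse), with the Mantel-Haenszel risk difference and 95% CI.
- Report each type's risk difference with 95% CI beside it, plus a test of interaction, stated in advance to be low-powered.
- Tabulate how many generalized controls received each of the two control drugs, so that readers can see what the generalized contrast contains.

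The cost is SAP wording and one form field, with no added patients. About 1 point of power is lost if type is not prognostic. Stratifying allocation by type is optional: it would limit imbalance, but it changes the randomization procedure at three hospitals. If it is adopted, the stratified test matters more. With null rates of 0.90/0.50, the pooled chi-square then rejects in only 2.9% to 3.4% of trials, while CMH stays near 5%.

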Randomized studies in drug-resistant epilepsy typically involve addition of new anti-epileptic drugs. However, in clinical practice, if the patient is already taking multiple drugs, then substitution of one of the current medications commonly occurs, despite little evidence supporting this approach.²² The choice of the substitution drug depends on the mechanism of action, the pharmacokinetic profile, drug-drug interaction, and the risk of seizure exacerbation as well as patients-related factors. The new combination is intended to maximize efficacy and minimize toxicity. However, the availability and cost-effectiveness should also be

taken into consideration since the patient would not reach the goal of ideal combination of drugs if they could not afford it nor even get the medication. ²³⁻²⁶ Another considerable case is one of drug resistance patterns in which at the first-time patients may not responsive to treatment yet they change into a state that is responsive to the medication. ²⁷ The choice of substitution therapy may originate from firs-line AEDs since evidences have shown they have equal efficacy to those of second-line ones. However, there is still lack of evidence whether the drug resistance pattern occur if the substitution drug is originated from first-line AED even more if it has ever been given prior to the current drug combination. ²⁷ The study aims to analyzed the efficacy and safety of first-line AEDs as substitution therapy in drug-resistant epilepsy children.

Primary Objective

The primary outcome of the research is to analyze the proportion of responders, who are defined as subjects who get 50% of seizure reduction.

Secondary Objectives

There are some secondary objectives of the study. The first one is to analyze the differences of improvement of quality of life, EEG feature and time to achieve seizure reduction, between the intervention and the control group. Besides, the research will describe the clinical characteristics, adverse effects of the drugs and laboratory features related to the adverse effects, among children with drug-resistant epilepsy. Furthermore, it will explain factors influencing the reduction of seizure frequency

Study Design

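### Completing the study and a 50% seizure reduction both define a responder, and the completers-only per-protocol set removes children because treatment failed

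*Combined protocol and SAP*

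**What the plan says.** Three places define the responder.

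- Primary Objective: the outcome is "the proportion of responders, who are defined as subjects who get 50% of seizure reduction".
- Outcome evaluation, item a: "Responder: there is a decrease in the frequency of seizures by 50% or more than before". Children with unchanged, insufficiently reduced or increased frequency are non-responders, and the reference is the initial frequency.
- Study procedure: "The children who complete all of the phases are categorized as responder". This sentence carries no seizure threshold.

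Study procedure also controls who completes. The intervention is ended "if the seizures increase more than one and a half time of the previous frequency", and of those children it says: "The subjects are categorized as non-responder, and will be dropped-out". Entry to the last phase is worded differently: "On the contrary, if the condition is better, then the children go to the maintenance of new combination".

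Analysis sets appear only under Statistical Analysis item 3, the absolute risk reduction (ARR), which is also called a primary outcome. Its event is a rise in seizures ("CER: the incidence of increased seizure frequency in the standard therapy group"). There the plan says: "This test will use 2 analyses known as intention to treat analysis and per-protocol analysis". Intention to treat keeps all randomised children as allocated. Per-protocol keeps only those who finish. Item 1, the chi-square test of responder proportions, names no analysis set.

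**The concern.** The primary endpoint has two definitions that need not agree, in an open-label trial, and nothing ranks them. An analyst could choose between them after seeing the data.

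The per-protocol set adds a second problem. Children whose seizures rise past the limit are dropped, and the per-protocol set then excludes them for not finishing. They leave because they failed, so the set is selected on the outcome it is meant to measure. For the ARR, the completers-only event rates lose every seizure increase that caused the intervention to be ended.

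**Working it through.** **Inputs.** Responder rates r = 0.95 (first-line) and 0.70 (control) and n = 50 per arm, all from Sample size. The documents do not give the share k of children with less than 50% reduction who still complete. I treat k as an assumption from 0 to 1, equal in both arms, with every child who has a 50% reduction completing and no other drop-out.

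**The plan's own figure.** With the printed Q1 = 0.5, the formula gives [(1.96√0.28875 + 0.84√0.685)/0.25]² = [(1.053 + 0.695)/0.25]² = 48.9, close to the stated 49.56. Since 1 − 0.95 = 0.05, the corrected term is √0.2575 and the result is 35.0. That slip is a separate matter, but it explains why power at 50 per arm starts well above 80% below.

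**Formulas.**
- All randomised, completion rule: r + (1 − r)k. The difference is 0.25(1 − k).
- Completers only, 50% rule: r / [r + (1 − r)k].
- Completers only, completion rule: 100% in both arms at every k.
- Expected completers per arm: 50[r + (1 − r)k].

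| k | All randomised, completion rule | Difference | Power | Completers only, 50% rule | Difference | Completers per arm |
|---|---|---|---|---|---|---|
| 0 | 95.0% vs 70.0% | 25.0 | 94.8% | 100% vs 100% | 0 | 47.5 vs 35.0 |
| 0.25 | 96.3% vs 77.5% | 18.8 | 85.1% | 98.7% vs 90.3% | 8.4 | 48.1 vs 38.8 |
| 0.5 | 97.5% vs 85.0% | 12.5 | 63.2% | 97.4% vs 82.4% | 15.1 | 48.8 vs 42.5 |
| 1 | 100% vs 100% | 0 | n/a | 95.0% vs 70.0% | 25.0 | 50 vs 50 |

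Differences are in percentage points. Power is by exact enumeration of the uncorrected chi-square test, two-sided 5%. A normal approximation gives 92%, 80% and 60% for the first three rows, the same pattern. Under the 50% rule the all-randomised result stays at 95% vs 70% whatever k is.

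**Two single-child checks against the wording.**
- Seizures per month 10, then 5, then 7. The rise is 7/5 = 1.4 times, below the 1.5-times limit. Against the start, 7/10 is a 30% reduction. If this child is allowed to complete, Study procedure says responder and Outcome evaluation says non-responder.
- Seizures per month 10, then 2, then 4. If the previous frequency means that of the preceding phase, the rise is 4/2 = 2 times and the intervention is ended, so Study procedure says non-responder. Against the start, 4/10 is a 60% reduction, which Outcome evaluation calls a responder. This conflict needs no assumption about k.

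**ARR.** The per-protocol ARR is forced to 0 only if no completer has an increased frequency. Otherwise it is not zero by construction, but it still omits the increases that led to ending.

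**The case against.** The strongest reply reads the completion sentence within its sequence. The dose is titrated until seizures have halved, tapering follows, and only children who are better enter the last phase with seizures no longer rising. On that reading a completer has reached 50% and kept it, so the sentence summarises the outcome definition. An analyst would in any case tend to follow the outcome section over procedural text. This is the k = 0 row, and it is a fair reading. It does not settle the matter. The text gives no route for a child who never reaches 50% or who rises by 1.0 to 1.5 times, and it neither lets that child complete nor excludes it. Even at k = 0 the completers-only response is 100% in both arms, and the 10, 2, 4 child can still be labelled both ways. Figures 1 and 2 were not available to this review and might show the missing branch.

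A second reply is that intention to treat protects the result, and that a per-protocol responder analysis may not be planned at all, since the analysis sets are described under item 3. Intention to treat does limit the damage: it keeps all randomised children, and ended children are labelled non-responders. However, its list of failures names the untreated, the lost and the crossed-over, and omits children ended for seizure increase. It also inherits whichever responder label is used, and it is not assigned to item 1.

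A third reply stands in part. The sizes are illustrative because k has no source. Item 1 also moves to a Fisher-type test when chi-square requirements fail. At k = 0.5 the expected non-responders are 50 × (0.025 + 0.150)/2 = 4.4 per arm. If the requirement is an expected count of 5, power with that switch is about 53%, so 63% understates the loss.

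**Conclusion.** The concern holds, and the primary endpoint definition must be settled before analysis. Confidence is high that the definitions conflict as written and that the per-protocol set is selected on outcome. The size depends on k, which is assumed. With k above 0, the primary difference depends on which section is followed: 18.8 points at k = 0.25 and 12.5 at k = 0.5, against 25 under the 50% rule. With k = 0, a per-protocol responder comparison is 100% vs 100% and carries no information. The intention-to-treat analysis is not degenerate, except under the completion rule at the extreme k = 1, but nothing makes it the main analysis of the responder proportion.

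**What to change.** 1. Delete the Study procedure sentence that equates completing with responding.
2. Apply the Outcome evaluation item a definition to every randomised child. State which month supplies the end-of-study frequency, so that it fits the phase timeline; item a says frequency is monthly but not which month.
3. State in item a and in the Statistical Analysis that a child whose intervention was ended for seizure increase is a non-responder in both analysis sets.
4. Name intention to treat as the main analysis for the item 1 responder test.
5. Define per-protocol by adherence and major protocol deviations, not by completion.
6. Reconcile the wording of the 1.5-times trigger, including what the previous frequency refers to, with the wording on entry to the last phase, so that every child has a stated path. The clinical rule is for the sponsor to decide.

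The cost is protocol and SAP wording only. The one downside is that per-protocol response rates will be lower and look less favourable.
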